#### **Survey Study**

The current study is a one-time survey of up to 1000 predominantly homeless adults accessing services at the Homeless Alliance Day Shelter ([name]

[name]). A convenience sample of unique shelter guests will be surveyed on several days each month over a one-year period, to understand the needs of users in light of seasonal and financial factors that vary over the days of the month (e.g., government paychecks) and months of the year (e.g., seasonal variations in temperature/weather). Study staff will be stationed near the entrance of the day shelter to provide information about the study and answer questions. Day Shelter guests who are present at the time when study staff are also present will be approached for participation in the study (or they may approach us). Study staff will plan to enroll unique survey participants (i.e., participants may not participate in the survey twice).

### **(Survey Study; pre-COVID – Before March 2020)**

Those enrolled will complete a 30-minute survey on a tablet computer at the day shelter. Study staff may read the survey questions to the participant and assist them in selecting answers on the tablet computer. Participants may be provided with reading glasses as needed. Participants will provide information on many factors related to homelessness including sociodemographic information, stress and discrimination, substance use, mental health history, social support, and criminal justice involvement (see survey questionnaire for a full list of questions asked during the survey study). Participants will be provided with a \$10 gift card.

### **Sub-Study.**

Overview. The sub-study will examine the feasibility and preliminary efficacy of providing financial incentives for combustible cigarette abstinence in combination with switching to e-cigarettes among 60 socioeconomically disadvantaged Homeless Alliance day shelter users. A total of 60 adults who access the day shelter will be recruited to participate in the sub-study. Participants will be randomly assigned to one of two groups and followed weekly from 1 week prior to switching through 4 weeks after switching, with a final 8-week post-switch follow-up. The intervention groups are 1) switching to e-cigarettes (EC), or 2) small financial incentives for cigarette abstinence + switching to e-cigarettes (FI + EC). Payments will be made via Greenphire clincard, which is similar to a debit card. The primary outcome will be carbon monoxide (CO)-verified combustible cigarette abstinence (CO) at 4- and 8-weeks post-switch date. Combustible cigarette reduction, EC use/switching, and dual use (cigarettes and ECs) will also be examined.

**Intervention Groups.** All participants will have the opportunity to earn \$20 for completing study assessments at visits 2 through 7 and \$50 for completing visit 8 (see Table 1).

Financial Incentives + E-Cigarettes (FI + EC). At baseline (1-week pre-switch), participants assigned to this group will be provided with an e-cigarette device and they will be offered 7 pods to try. Participants will be encouraged to practice using the device over the subsequent week (before they switch to exclusive use). Participants will be advised to completely switch from combustible cigarettes to

the e-cigarette device one week after the baseline visit. On the switch date, they will be supplied with refill cartridges in the flavor(s) of their choice and based on their pre-switch smoking level. One pod ≈ 200 puffs and provides the amount of nicotine in ≈ 1 pack of cigarettes. Thus, someone who smokes a pack of cigarettes each day may be expected to use about 1 pod per day.

Participants in this group can also earn financial incentives for combustible cigarette abstinence. Financial incentives will be earned based on self-reported cigarette abstinence and carbon monoxide readings. Beginning with a \$20 payment for self-reporting exclusive e-cigarette use during the past 24 hours along with a CO reading of ≤8 ppm on the specified switch day (i.e., one week after the enrollment visit), with this amount increasing by \$5 with each successive weekly self-report of cigarette abstinence along with a CO reading of ≤6 ppm (i.e., up to \$40 in Greenphire clincard payments at 4 weeks post-switch; \$150 total; see Table 1). After the switch day, participants with CO readings > 6 ppm will not earn the payment for that week, and the payment will reset to the starting incentive of \$20.

**e-Cigarettes (EC).** Participants assigned to EC will receive the e-cigarette device and the same instructions described previously. Participants in the EC group will not earn incentives for cigarette abstinence, rather they will be yoked to a participant assigned to the (FI + EC) group and will receive the payment earned by that FI + EC participant (up to \$150 total). Yoking will reduce or eliminate differential attendance rates between groups because participants can earn the same amount of money regardless of group assignment.

**Safety Protocol for COVID-19.** Data collection may take place inside the Homeless Alliance or outside in the homeless alliance courtyard. Participants may be asked to wear a mask while completing the survey and other study requirements. If participants do not have a mask then one may be provided to them. Hand sanitizer will be available to participants and staff. Depending on community transmission rates of COVID-19 and the comfort level of the staff, CO breath sample collection may take place outside in the courtyard. In addition, the number of participants who can be surveyed at once may be limited and social distancing guidelines may be implemented. All equipment will be wiped down following each use. Staff may wear masks while interacting with participants and handling equipment.

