**Switch Day (Visit 3; 1 week after baseline).** Participants will complete self-report questionnaires on a laptop computer; and expired CO and weight will be measured in a private area of the shelter to ensure confidentiality. Participants assigned to the FI + EC treatment will receive an additional \$20 paymentif their expired CO level is  $\leq 8$  ppm (please note that the less stringent cut-off of 8 ppm will be used to verify abstinence on the first post-switch day only, because of the recency of switching). EC participants will receive the same payment as their yoked FI + EC counterpart. Attempts will be made to contact participants who do not attend study visits, in order to obtain self-reported smoking status. Participants will be supplied with pods in the flavor(s) of their choice, based off of what research staff has available, and based on their pre-switch smoking level.

**1-4 Weeks Post-Switch (Visits 4-7).** Participants will complete self-report questionnaires on a laptop computer; and expired CO and weight will be measured in a private room to ensure confidentiality. Participants randomized to the + EC group will receive an additional \$20-\$40 credit for self-reported abstinence and CO readings  $\leq 6$  ppm. EC participants will receive the same payment as their yoked FI + EC counterpart. Additional pods will be provided at each weekly visit based on pre-switch smoking levels. Participants will be

provided with 1 additional e-cigarette device *only if* they lose or damage the first device. Participants will not be provided with any e-cigarette supplies after visit 7, to determine whether they continue to use the e-cigarette on their own.

**8 Weeks Post-Switch (Visit 8).** Participants will complete self-report questionnaires on a laptop computer; and expired CO and weight will be measured in a private area to ensure confidentiality. Participants will receive a \$50 for completing this final follow-up visit, and participants may keep their study phones. Participants will be advised that they can receive free smoking cessation treatment through the Tobacco Treatment Research Program^36 or the Oklahoma Tobacco Helpline and provided with contact information.

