### **E. Statistical Methods**

**Survey Study.** Day shelter guests (up to 1000) using shelter services will have the opportunity to participate in the survey study. Study staff will enroll unique participants each month (i.e., participants may participate only once). Descriptive statistics will be generated (e.g., frequencies, means) to describe the characteristics, needs, tobacco use history, and tobacco treatment preferences of study participants, along with correlation and regression analyses to identify cross-sectional relationships among variables. For example, we will examine the percent of individuals who have used e-cigarettes as a means of quitting smoking as well as the percent who are interested in switching to e-cigarettes in the future. Tobacco use history and preferences for tobacco cessation treatment will be described (e.g., means, frequencies). The relations between tobacco use and health, other health behaviors, sociodemographic (e.g., education, race/ethnicity, gender), and personal characteristics (e.g., stress and mental health) will be examined via correlation and regression analyses. The rate of missing data and missing data patterns will be examined before analysis. If the combined missing rate is very small, say less than 5%, then we may safely perform the data analysis on the available data. If the missing rate is high, then we will explore sequential multiple imputation (SMI) as described by Raghunathan et al. The analysis results from SMI data will be compared with those from the available data.

**Sub-Study.** A sub-sample of survey participants ( $N = 60$ ) who are currently smoking cigarettes will be randomized to one of two intervention groups and followed for ten weeks (2-weeks pre-switch through 8-weeks post-switch). This pilot study will provide feasibility data and intervention effect sizes for the power analysis for a future fully-powered randomized controlled trial. Descriptive statistics will be employed (e.g., frequencies, means) to characterize combustible cigarette cessation, cigarette reduction, daily EC use, and dual EC and combustible cigarette use. The intervention groups will be compared on CO-verified cigarette abstinence at 4 and 8 weeks after a scheduled switch attempt using logistic regression analysis. Secondary analyses will focus on reductions in cigarette smoking, EC use/switching, and dual use of ECs and combustible cigarettes.

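### Do two unranked primary time points (weeks 4 and 8), with no error control, call for a change to the sub-study plan?

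*Combined protocol and SAP*

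**What the plan says.** Section D, Sub-Study overview: "The primary outcome will be carbon monoxide (CO)-verified combustible cigarette abstinence (CO) at 4- and 8-weeks post-switch date". Section E, Sub-Study: "The intervention groups will be compared on CO-verified cigarette abstinence at 4 and 8 weeks after a scheduled switch attempt using logistic regression analysis". No section names a leading time point, a significance level, a success rule, a testing order, a joint model or a multiplicity adjustment.

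The two readings are taken under different conditions. At week 4 (visit 7), Table 1 and the text on visits 4-7 allow an FI + EC participant up to $40, a "credit for self-reported abstinence and CO readings" at or below 6 ppm. Through yoking, an EC participant receives whatever the paired FI + EC participant earned, regardless of the EC participant's own reading. At week 8 (visit 8) the incentive/yoking column shows $0, and both arms get $50 for the assessment. Pod supply has also ended in both arms by then: "Participants will not be provided with any e-cigarette supplies after visit 7, to determine whether they continue to use the e-cigarette on their own".

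On purpose, Section E says: "This pilot study will provide feasibility data and intervention effect sizes for the power analysis for a future fully-powered randomized controlled trial". Section D says: "The sub-study will examine the feasibility and preliminary efficacy of providing financial incentives for combustible cigarette abstinence". On size, Section D says only: "A total of 60 adults who access the day shelter will be recruited to participate in the sub-study". No calculation supports that number.

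**The concern.** Two comparisons carry the label primary and neither leads. The hypothesis in Section A expects FI + EC to do better but names no time point, so a favourable result at either visit could be presented as confirming it. Under the usual 0.05 convention that raises the chance of a false positive above 5%.

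The two readings also answer different questions. At week 4 the FI + EC participant's own reading decides a payment. At week 8 no reading does, and supplies have stopped. If the larger of the two estimates were carried into the next trial's power calculation, that trial could be planned on an optimistic effect, or on an effect seen only while payments run.

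**Working it through.** **Inputs.** From the documents: two time points, logistic regression at each, 60 participants. Assumed, because the documents are silent: two-sided 0.05 per test, success claimed if either test is positive, 30 per arm, and the abstinence rates shown below. The plan gives no error rate or power of its own to reproduce.

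**1. Error rate under the assumed either-time rule.** For independent tests it is 1 − 0.95² = 0.0975. For test statistics with correlation ρ it is 1 − P(|Z₁| < 1.96 and |Z₂| < 1.96) from the bivariate normal:

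| ρ | At least one false positive | Favouring FI + EC only |
|---|---|---|
| 0 | 9.75% | 4.9% |
| 0.3 | 9.5% | 4.8% |
| 0.5 | 9.1% | 4.5% |
| 0.7 | 8.4% | 4.2% |
| 0.9 | 7.0% | 3.5% |

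The nominal values are 5% and 2.5%. The inflation factor runs from 9.75/5 = 1.95 down to 7.04/5 = 1.41. The same people give the same measure four weeks apart, so positive correlation is expected and a near-doubling is the extreme case.

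**2. The same rule with 30 per arm.** In a simulation of 200,000 trials per setting (null abstinence 10% to 30%, within-person correlation 0 to 0.7), the either-time error was 9.6% to 14.5% with likelihood-ratio tests and 1.5% to 8.0% with Wald tests. Single likelihood-ratio tests already ran at 5.7% to 7.6%. With 10% abstinence at both times, likelihood-ratio tests at 0.025 each still gave 6.5% to 7.5%, while unadjusted Wald tests gave 1.5% to 1.7%. At this sample size the choice of test statistic moves the error rate at least as much as the second time point does.

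**3. An effect present only while incentives run.** Take 40% against 15% at week 4, and 15% in both arms at week 8. An either-time rule is positive in 57% (Wald) to 65% (likelihood ratio) of trials. Week 4 alone is positive in 56% to 63%. The second look adds about 1 to 3 percentage points; nearly all the positives reflect a real week-4 effect.

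**4. Price of strict control.** Power with 30 per arm, at 0.05 and at 0.025 (Bonferroni, also the first step of Holm):

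| Abstinence, EC vs FI + EC | 0.05 | 0.025 |
|---|---|---|
| 10% vs 30% | 49% | 38% |
| 15% vs 40% | 59% | 47% |
| 10% vs 40% | 78% | 68% |

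**5. Bias from carrying forward the larger estimate.** If the true effects are equal and each estimate has standard error SE, the larger of the two exceeds the truth on average by SE × √((1 − ρ)/π). With 20% abstinence and 30 per arm, SE = √(2 × 0.2 × 0.8/30) = 10.3 percentage points. At ρ = 0.7 the excess is 10.3 × √(0.3/3.1416) = 3.2 points; at ρ = 0 it is 5.8 points. The 95% half-width of either estimate is 1.96 × 10.3 = 20 points. The selection bias is real but small beside the imprecision that any user of this pilot must already allow for.

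**The case for a change.** The strongest case for a change is that being a pilot does not settle the matter. The plan claims preliminary efficacy and will hand effect sizes to a later power analysis, so picking the better of two unranked results after seeing them would mislead without any p-value being involved. Naming one time point in advance would cost a sentence and no power.

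Part of this stands. The plan does not rank the two readings, and stating in advance which one will feed the next trial would be tidier. The rest is weaker. The either-time rule is inferred from silence; nothing in the documents says that one positive result is enough. Nothing is pooled either, since Section E compares the arms at each time. The arms are not paid differently at week 4: yoking gives EC the same amount, and what differs is whether the participant's own reading earns it. That contingency is the randomised intervention, so the week-4 contrast is the effect under study and not a contaminant. The overview in Section D also gives the later visit its own purpose, to see whether e-cigarette use persists without supplies, although it says this of supplies and not of incentives.

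Which reading should lead is open to fair disagreement. Week 4 shows the incentive at work. Week 8 follows the end of both incentives and supplies, so it measures persistence and not the incentive alone.

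**Conclusion.** The observation is accurate: there are two primary time points with no ranking and no error control. It does not make the plan unsound for its stated purpose. The 7% to 10% error rate depends on a 0.05 level and an either-time success rule that the documents do not contain, and on large-sample theory that 30 per arm does not closely follow. Followed as written, the plan gives two distinct estimates at known visits. Analysts would report both with confidence intervals and describe week 4 as on-incentive and week 8 as after incentives and supplies end. Designers of the later trial would then use the estimate that matches their own endpoint. A formal adjustment would lower power by 10 to 12 percentage points in the scenarios above and would not improve either estimate. This is an unstated detail together with a fair trade-off, and no change is needed. The conclusion would differ if the sub-study were presented as a confirmatory test of efficacy.

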#### **D. Research Design and Methods**

**Overview.** The current protocol includes a parent survey study, and an intervention sub-study. The parent survey study will assess the characteristics and needs of Homeless Alliance Day Shelter users (up to 1000 adults), 2) characterize tobacco and e-cigarette use patterns, tobacco history, and past cessation attempts among individuals accessing services at the Homeless Alliance Day Shelter, and 3) assess interest in tobacco cessation and harm reduction intervention approaches. Based on responses to screening items assessing eligibility criteria, participants will be identified as eligible for the sub-study. The sub-study ( $N = 60$ ) will 4) characterize reductions in cigarette smoking, smoking abstinence, e-cigarette dual use, and e-cigarette use/switching following randomization to: 1) an e-cigarette device and supplies (device charger, pods) for 4 weeks, or 2) e-cigarette and supplies for 4 weeks + financial incentives for combustible cigarette abstinence among Homeless Alliance Day Shelter guests. Participants will be followed through 8 weeks post-switch date to determine whether they continue to use e-cigarettes when the supplies are no longer provided. Both the parent survey study and intervention sub-study will provide data related to tobacco use, which will be used to support future grant funding applications. Both components of the study will take place at the Homeless Alliance Day Shelter.

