### **Sub-Study Visits.**

**Recruitment/Screening (Visit 1, Screening & Scheduling).** Eligible participants who complete the screening survey will be given a chance to review the consent form. Study staff will provide the participant with ample time to review the study information and ask questions related to their participation. Participants who enroll will be scheduled to return for a baseline visit (typically within the next 7 days). The Homeless Shelter Alliance case workers, who work

with the shelter's guests, may encourage their clients to enroll and retain participation in the study.

**Baseline (Visit 2).** Enrolled participants will be randomly assigned to the EC or FI + EC condition. Enrolled participants will be asked to provide their personal information (name and phone numbers). Participants will be instructed to switch from combustible cigarettes to e-cigarettes at bedtime or 10:00 pm (whichever occurs first), on the evening prior to their next scheduled weekly session. They will be provided with a EC device and they will have the opportunity to try it out. They will be provided with 7 pods (5% nicotine).. They will keep the pods in order to practice using the e-cigarette device over the week prior to their switch date. Participants will be advised about earning financial incentives for switching to ECs or yoking) beginning the following week on the quit/switch day. The schedule of payments will be discussed with all participants (see Table 1). Participants will be instructed not to use THC-containing vaping products and "street" vaping products, and not to modify or add chemicals to their vaping supplies while they are enrolled in the study. They will be counseled to use only the supplies that they are given by study staff, and to avoid dual use of e-cigarettes and cigarettes or other combustible products, including marijuana. Participants will receive a \$10 Greenphire clincard paymentfor completing this visit and they will be provided with a Tracfone (or similar "burner" phone) along with a prepaid phone plan that will cover the study period to facilitate communication between the participant and study staff. Participants will be encouraged to complete this visit as soon as possible, but it can be completed within 21 days of visit 1. Enrollment into the sub-study will cease once 60 participants are enrolled.

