**Table 1. Sub-study compensation schedule.**

	Assessments	Incentive/ Yoking	Total Possible Earnings
Visit 1 (Brief Screening)	\$0	\$0	\$0
Visit 2 (baseline/enrollment; 1 week pre-switch)	\$20	\$0	\$20
Visit 3 (switch Day)	\$20	\$20	\$40
Visit 4 (1-week post-switch)	\$20	up to \$25	\$45
Visit 5 (2 weeks post-switch)	\$20	up to \$30	\$50
Visit 6 (3 weeks post-switch)	\$20	up to \$35	\$55
Visit 7 (4 weeks post-switch)	\$20	up to \$40	\$60
Visit 8 (8 weeks post-switch)	\$50	\$0	\$50
Total Possible Earnings	\$170	\$150	\$320

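### The Visit 3 incentive rule is internally inconsistent: its 24-hour look-back reaches back before the instructed evening-before switch, and the visit procedure omits it (minor)

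*Combined protocol and SAP*

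**What the plan says.** All the relevant text is in section D of the combined protocol and SAP.

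- **Sub-Study, Intervention Groups (FI + EC), general rule:** "Financial incentives will be earned based on self-reported cigarette abstinence and carbon monoxide readings".
- **Same place, first payment:** $20 for "self-reporting exclusive e-cigarette use during the past 24 hours along with a CO reading of ≤8 ppm on the specified switch day".
- **Same place, later payments:** the amount rises by $5 "with each successive weekly self-report of cigarette abstinence along with a CO reading of ≤6 ppm", to a stated maximum of $40 at week 4 and $150 overall. After the switch day, a CO above 6 ppm forfeits that week's payment and returns the amount to $20.
- **Same place, week before the switch:** participants are "encouraged to practice using the device over the subsequent week (before they switch to exclusive use").
- **Sub-Study Visits, Baseline (Visit 2):** the switch instruction reads "switch from combustible cigarettes to e-cigarettes at bedtime or 10:00 pm (whichever occurs first), on the evening prior to their next scheduled weekly session". Participants are also advised about earning incentives, and "The schedule of payments will be discussed with all participants (see Table 1"). The "Visit 3 (switch Day")" row of Table 1 lists amounts only.
- **Sub-Study Visits, Switch Day (Visit 3):** the $20 is conditioned on CO of 8 ppm or less. No self-report condition or look-back appears. The looser CO limit is explained by how recently participants will have switched. EC participants receive whatever their yoked FI + EC partner receives.
- **Overview, setting:** "Both components of the study will take place at the Homeless Alliance Day Shelter". No clock time is given for Visit 3.

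**The concern.** The instructed stop time and the rewarded period do not match. The latest instructed stop is 10 pm on the evening before the visit, but the Intervention Groups text asks for a full 24 hours without cigarettes. A participant who uses the practice week as described, stops when told and answers honestly is refused the first reward. One who reports 24 hours inaccurately and has a CO of 8 ppm or less is paid. The Switch Day procedure omits the 24-hour condition, so staff working from the two places could decide the same case differently.

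Contingent payment is what separates FI + EC from EC, and this is the first time it is delivered. Section E says the pilot is to supply feasibility data and effect sizes for a later trial. A reader of those results should be able to tell which incentive schedule was applied.

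**Working it through.** **1. Reproduce the plan's figures (Table 1).**

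- Incentives: 20 + 25 + 30 + 35 + 40 = $150, as stated.
- Assessments: 6 × 20 + 50 = $170.
- Total: 150 + 170 = $320, as stated.

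**2. Hours since the instructed switch.** Elapsed hours = (24 − stop hour) + visit hour, on a 24-hour clock. The 10 pm stop is from the Baseline (Visit 2) text. The 8 pm bedtime and the visit times are assumptions, since the documents give neither.

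| Visit 3 time (assumed) | Stop at 10 pm | Stop at 8 pm (assumed bedtime) |
|---|---|---|
| 8 am | 2 + 8 = 10 h | 4 + 8 = 12 h |
| noon | 2 + 12 = 14 h | 4 + 12 = 16 h |
| 5 pm | 2 + 17 = 19 h | 4 + 17 = 21 h |

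All six cells are below 24 h. The shortfall runs from 24 − 21 = 3 h to 24 − 10 = 14 h. The window is met only if the visit takes place at or after the previous evening's stop time, that is, 10 pm for a 10 pm stop or 8 pm for an 8 pm stop.

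**3. Effect on the incentive maximum.** This applies to a participant who smoked until the instructed time, has a CO of 8 ppm or less at Visit 3, reports truthfully and meets every later condition.

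| Reading | Visits 3 to 7 | Incentive maximum | Loss | With assessments |
|---|---|---|---|---|
| Switch Day wording, CO only | 20 + 25 + 30 + 35 + 40 | $150 | $0 | $320 |
| 24-hour rule, Visit 4 stays at $25 | 0 + 25 + 30 + 35 + 40 | $130 | $20 (20/150 = 13%) | 130 + 170 = $300 |
| 24-hour rule, Visit 4 starts at $20 | 0 + 20 + 25 + 30 + 35 | $110 | $40 (40/150 = 27%) | 110 + 170 = $280 |

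**4. Which reading does the text select?** None with certainty. The word *successive* in the escalation sentence favours a start at $20 at Visit 4. But the only explicit reset rule is confined to CO failures after the switch day, and a self-report shortfall on the switch day is neither. The $20 to $40 range quoted for Visits 4 to 7 does not settle it, because resets after later failures would produce the same range.

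**The case against.** The strongest reply is that the Switch Day (Visit 3) procedure governs what happens at that visit. It pays on CO alone and loosens the limit precisely because participants have only just switched. It therefore expects to pay people who followed the instruction, and under it nobody loses anything. This stands as a reason not to assume that payments would be withheld. It does not remove the inconsistency. The general rule in Intervention Groups rests payment on self-report and CO together, and section G describes CO as confirming self-reported status. The Switch Day sentence may therefore be shorthand that still assumes a self-report, but it gives no look-back for one.

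A second reply is that participants are counselled to avoid dual use and are told about the incentives at baseline, so some will stop earlier than instructed. That is correct, and anyone who stops at least 24 hours before the visit can still earn the full $150. How the dual-use advice applies during the practice week is unclear. It does not cancel a specific switch time that follows a week of practice.

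A reader might also infer that the incentive ceiling is really $110, or that the efficacy comparison is compromised. The documents support neither. The $110 figure is one end of a range that includes no loss. The primary outcome is CO-verified abstinence at 4 and 8 weeks, which Visit 3 status does not define. Later payments remain available, yoking keeps pay equal between arms, and nothing in the plan allows an effect on the estimated effect size to be calculated.

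**Conclusion.** The inconsistency is real and minor. Three parts of section D give a look-back, a switch time and a visit procedure that do not agree, and nothing reconciles them. Under the 24-hour rule, a participant who smokes until the instructed time and attends in the daytime cannot truthfully earn the first $20. The loss against the $150 maximum is $0, $20 or $40 depending on the reading, and the yoked EC partner's pay changes by the same amount.

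This rests on a daytime Visit 3, which is a fair inference from the setting but is not stated, and on the participant smoking until the instructed time. The documents do not give the share of participants affected. The consequence is for early delivery of the incentive and for describing the schedule clearly. The definition of the primary outcome is untouched. Nothing suggests that the sponsor meant to exclude people who switched as instructed; the allowance for recent switching points to an oversight in the wording.

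**What to change.** State one Visit 3 rule, in identical words, in Intervention Groups (FI + EC) and in Switch Day (Visit 3): the participant reports no combustible cigarettes since the instructed switch time (bedtime or 10 pm the evening before, whichever came first) and has a CO of 8 ppm or less. Add one sentence saying what Visit 4 pays if the Visit 3 payment was not earned, either $20 or $25.

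The cost is a short wording amendment, with no extra visits, staff or participants. The same amendment could correct the Visit 2 assessment payment, which is $10 in the Baseline text but $20 in Intervention Groups and Table 1. That is a separate correction and carries no weight in this point.
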